#### Proteinuria by Urinalysis (Dipstick)

Treatment-emergent proteinuria by urinalysis (dipstick) over time will be summarized by intervention arm. Cross-tabulation of grades overtime versus baseline will also be presented.

#### Other Renal Biomarkers

Selected renal biomarkers RBP and beta-2-microglobulin, RBP to creatinine ratio and beta-2-microglobulin to creatinine ratio will be summarized by intervention arm and visit using descriptive statistics.

The number and proportion of participants with beta-2-microglobulin to creatinine ratio ≤343.5 µg/g and >343.5 µg/g will be tabulated over time.

The number and proportion of participants with retinal binding protein to creatinine ratio results in the following categories overtime will be tabulated:

- < 50 years of age: < 130 mcg/g creatinine, ≥ 130 mcg/g creatinine
- ≥ 50 years of age: < 172 mcg/g creatinine, ≥ 172 mcg/g creatinine

#### Phosphate excretion

Other renal biomarkers include FEPO4 that will be summarized by intervention arm and visit using descriptive statistics.

FEPO4 will be calculated as follows:

- Based on unadjusted serum creatinine:  

$$\text{FEPO4 (\%)} = (\text{SCr} \times \text{UPO4}) / (\text{SPO4} \times \text{UCr}) \times 100 (\%)$$

Where SCr is serum creatinine concentration, UPO4 is urine phosphate concentration, SPO4 is serum phosphate concentration, and UCr is urine creatinine concentration.

The proportions of participants with FEPO4  $\leq 10\%$  and  $>10\%$  will be tabulated.

The baseline, post-baseline, and change from baseline in FEPO4 will be summarized by intervention arm and visit using descriptive statistics. Median (Q1, Q3) change from baseline in FEPO4 over time will be plotted by intervention arm.

### **Subclinical renal proximal tubulopathy**

Potential Markers of Renal Proximal Tubulopathy are:

1. Confirmed increase in serum creatinine  $\geq 0.40$  mg/dL from baseline.
2. Confirmed  $\geq 2$  grade level increase from baseline in graded proteinuria
3. Confirmed  $\geq 1$  grade level increase from baseline in graded hypophosphatemia
4. Confirmed  $\geq 1$  grade level increase from baseline in graded glycosuria concurrent with serum glucose  $\leq 100$  mg/dL (normoglycemic glycosuria)

A confirmed laboratory abnormality is defined as an abnormality observed at 2 consecutive post-baseline measurements or an abnormality observed at 1 post-baseline measurement followed by study drug discontinuation.

A subclinical renal proximal tubulopathy will be defined as confirmed abnormalities in any 2 out of the 4 renal parameters (serum creatinine and one or more of the 3 other markers of tubular dysfunction).

### **Baseline Subclinical renal proximal tubulopathy**

Potential Markers of Renal Proximal Tubulopathy at Baseline

1. Grade  $\geq 1$  serum creatinine
2. Grade  $\geq 2$  proteinuria
3. Grade  $\geq 1$  hypophosphatemia
4. Grade  $\geq 1$  glycosuria concurrent with serum glucose  $\leq 100$  mg/dL (normoglycemic glycosuria)

A baseline subclinical renal proximal tubulopathy will be defined as abnormalities in 2 out of the 4 renal parameters (serum creatinine + 1 or more of the 3 other markers of tubular dysfunction).

### **5.6.3.3. Vital Signs**

The following parameters measurements will be analyzed:

- Supine pulse rate (bpm)
- Supine systolic blood pressure (mmHg)
- Supine diastolic blood pressure (mmHg)

- Body temperature (°C)

The abnormalities in vital signs will be determined according to the criteria specified in the Cardiovascular Safety – Abnormalities Table (see Clinical Protocol Appendix 8).

An assessment is treatment-emergent if abnormality worsened as compared to the abnormality at baseline; this also includes the shift from abnormally high to abnormally low and vice-versa. Post-baseline abnormalities are always treatment-emergent with regard to missing abnormalities at baseline. The abnormally high values (i.e. abnormally high, grade 1 or mild, grade 2 or moderate, grade 3 or severe) versus the abnormally low values are considered equally important.

For each parameter, a “worst-case” analysis will be performed by using the worst abnormality and time point per participant. Worst-case will be derived within each analysis phase, including unscheduled assessments. In case the same participant has both abnormalities (low and high) for the same test within the same phase, the participant will be counted in the analysis for both abnormality directions (abnormally high and low).

Vital signs records with partial dates (any of day/month/year is missing) will not be used in the analysis but will be listed.

Descriptive statistics of continuous vital sign parameters and body temperature will be calculated for observed values and changes from baseline at each scheduled time point.

Shift tables will be provided summarizing the shift in vital sign and body temperature values from baseline over time with respect to abnormality criteria (low, normal, high) for each parameter by analysis phase.

A cross-tabulation of the worst abnormalities versus baseline per parameter and analysis phase will be presented including also the number of participants per abnormality, the number of participants with treatment emergent abnormalities per abnormality.

A tabulation of percentage and number of the participants who have treatment-emergent worst abnormalities per parameter and analysis phase will be included.

A listing including all parameters for participants with at least one treatment-emergent abnormality (on actual values or change from baseline) is provided. Additional vital signs assessments corresponding to the rash eCRF pages will be only listed as applicable.

The physical examination findings and abnormalities will be listed.

#### **5.6.3.4. Electrocardiogram**

Evaluation of the triplicate 12-lead ECGs will be based on the mean value of the triplicate parameters and the abnormalities will be defined on the triplicate means.

The ECG parameters that will be analyzed are heart rate (bpm), PR interval (ms), RR interval (ms), QRS interval (ms), QT interval (ms), and corrected QT (QTc) interval using the following correction methods:

Fridericia's formula:  $QTcF \text{ (msec)} = QT \text{ (msec)} / (RR \text{ (msec)}/1000)^{1/3}$ ; if RR is missing, use  $QT \text{ (msec)} * (HR(\text{bpm})/60)^{1/3}$ ;

The abnormalities in ECG parameters will be determined according to the criteria specified in the Cardiovascular Safety – Abnormalities Table (see Clinical Protocol Appendix 8, Cardiovascular Safety- Abnormalities Table). Abnormalities on actual values are provided for HR, PR, QRS and QTcF. Additional abnormalities on change from baseline will be provided for QTcF. No abnormalities will be defined for actual uncorrected QT values. Uncorrected QT  $\geq$  500 ms will be flagged and only shown in listings.

An assessment is treatment-emergent if abnormality worsened as compared to the abnormality at baseline; this also includes the shift from abnormally high to abnormally low and vice-versa. Post-reference abnormalities are always treatment-emergent with regard to missing abnormalities at baseline. The abnormally high values (i.e. abnormally high, borderline prolonged, prolonged, pathologically prolonged) versus the abnormally low values are considered equally important. Abnormalities defined on changes from baseline are always treatment-emergent.

For each parameter, a “worst-case” analysis will be performed by using the worst abnormality and time point per participant. Worst-case will be derived within each analysis phase, including unscheduled assessments. In case the same participant has both abnormalities (low and high) for the same test within the same phase, the participant will be counted in the analysis for both abnormality directions (abnormally high and low).

For the time points on which triplicate ECGs apply, a rounded mean value to the next integer per triplet will be calculated per time point before any further handling. This rounded mean value will be used through the entire analysis also in case of 1 or 2 missing values.

ECG records with partial dates (any of day/month/year is missing) will not be used in analysis, except in the listings. The following imputation rules will be applied.

If heart rate (HR) is missing, it will be calculated using RR (if available) and rounded to the integer value (see formula below) before any further handling if applicable.

$$\frac{1000}{RR(ms)} = \frac{HR(bpm)}{60}$$

HR from the vital signs section (i.e. pulse) will not be used in this ECG analysis section. RR values (if available) will only be listed. Recalculated HR values will be flagged.

Descriptive statistics will be calculated for observed values and changes from baseline per parameter (all parameters except for RR) at each scheduled time point by intervention arm and analysis phase.

Shift tables will be provided summarizing the shift in ECG values from baseline over time with respect to abnormality category (low, normal, high) for each parameter by analysis phase.

A cross-tabulation of the worst abnormalities (on actual values) versus baseline per parameter by analysis phase will be presented including also the number of participants per abnormality. A tabulation of number and percentage of the participants who have treatment-emergent worst abnormalities per parameter (i.e. for HR, PR, QRS and QTcF) and analysis phase will also be presented.

A cross-tabulation of the worst change from baseline abnormalities (i.e. for QTcF) versus the baseline category per parameter will be presented by intervention arm and analysis phase.

Frequency tabulations of categorized corrected QT/QTc change from baseline ( $\leq 30$  msec,  $>30$ - $\leq 60$  msec,  $>60$  msec) and categorized corrected QT/QTc interval values ( $\leq 450$  msec,  $>450$ - $\leq 480$  msec,  $>480$ - $\leq 500$  msec,  $>500$  msec) per timepoint will be presented by intervention arm.

Listings including all parameters for participants with at least one treatment-emergent abnormality (on actual values or change from baseline), including all findings (e.g. interpretation, rhythm, or technical findings) for participants with uncorrected QT values  $\geq 500$  ms will be provided separately.

#### **5.6.3.5. Physical and Ophthalmic Examinations**

The physical and ophthalmic examination findings and abnormalities will be listed. A listing of participants who experienced a decrease or loss of vision at any timepoint during study will be provided.

### **5.7. Other Analyses**

#### **5.7.1. Pharmacokinetics**

Population PK analysis of plasma concentration-time data of JNJ-73763976 (JNJ-3976), and JNJ-73763924 (JNJ-3924) may be performed using non-linear mixed effects modeling. Data from the current study may be combined with prior information available from Phase 1 and/or 2 studies to support a relevant structural model. Available baseline characteristics (e.g. demographics, laboratory variables, genotypes) may be included in the model as necessary. If a population PK analysis is conducted, the results will be presented either in the clinical study report or in a separate report.

#### **5.7.2. Pharmacokinetic/Pharmacodynamic Relationships**

Relationships of PK parameters for JNJ-3976 and JNJ-3924, and, optionally, for NA and PegIFN- $\alpha 2a$  with selected efficacy and with selected safety endpoints may be evaluated and graphically displayed, if applicable.

Modeling of key PD parameters (e.g. HBsAg, HBV DNA) may be performed using population PK/PD. If PK/PD modeling of key efficacy endpoints is performed, treatment effect and possible covariates may be investigated. Other biomarkers may be explored at the Sponsor's discretion. If applicable, the results will be described in a separate report.

### 5.7.3. Immune Analyses

Descriptive statistics (n, mean, SD, coefficient of variation [CV], geometric mean, median, minimum, and maximum) may be used to describe the magnitude of the gamma interferon (IFN- $\gamma$ ) T-cell response or the CD4+ and CD8+ T-cell responses (expressing at least 1 cytokine such as interleukin [IL]-2, TNF- $\alpha$  or IFN- $\gamma$  specific to any HBV antigen) as defined by ELISpot and/or ICS, respectively. Changes from baseline (or positivity threshold) will also be tabulated for PBMCs during study intervention and follow-up. The proportion (%) of chronic HBV-infected patients with detectable responses based on the magnitude of the IFN- $\gamma$  T-cell response or the CD4+ or CD8+ T-cells expressing at least 1 of the cytokines amongst IL-2, TNF- $\alpha$  or IFN- $\gamma$  for 1 of the HBV antigens as defined by ELISpot and/or ICS, respectively, will be determined. Changes from baseline (or positivity threshold) in HBV-specific peripheral blood T-cell responses will be summarized and tabulated.

Graphs showing the individual subject values as dots, together with horizontal lines indicating the corresponding median and interquartile range (IQR) per time point for each assay will be presented. The spaghetti plots will be used to show the patient profiles per time point for each assay. A graph showing the median and IQR over time by intervention arm will be presented. A bar chart will be used to show the breadth of response (i.e. HBV-specific immune response rate for combinations of peptide pools).

For intracellular cytokine staining (ICS), for all cytokine combinations (IFN $\gamma$  and/or TNF $\alpha$  and/or IL-2), pie charts will be presented to reflect the distribution of each of the cytokine combinations (i.e. the proportion of a specific cytokine combination of the CD4 or CD8 T-cells secreting at least one cytokine), and bar charts will be presented to reflect the mean magnitude of each combination.

### 5.7.4. Viral Genome Sequence Analysis

The sequencing of samples from participants in this study may be triggered by the sponsor virologist based on changes in HBV DNA levels observed in each individual subject and the limits of the sequencing assay.

Viral genome sequence analysis will be performed to evaluate the presence of genetic variations (including substitutions) associated with JNJ-3989, and/or ETV or TDF/TAF treatment on both nucleotide and/or amino acid level.

Sequencing of the HBV genome will be performed to monitor HBV variants present at the time points indicated in Section 5.7.4.1.

Virology results will be presented by specified timepoints and genetic region and position of interest. Exploratory viral sequencing may be performed using HBV RNA. A separate virology report will be prepared.

#### 5.7.4.1. Time Points and Samples

When analyzing sequencing data, the focus will be on genetic variants at

- Time Point of Sequence at Virologic Breakthrough: time point with sequence data available closest to the time point of virologic breakthrough (FTPT) (See Section 5.4.1.1.13 for virologic breakthrough definition)
- Time Point of Sequence at Virologic Flare: time point with sequence data available closest to the time point of Virologic flare (See Section 5.4.1.1.14 for virologic flare definition)
- Time Point of Sequence at Re-treatment during Post-treatment Follow-up: time point with sequence data available closest to time point where re-treatment criteria is met (See Section 5.4.1.1.1)
- Aggregated Post-Baseline Study Period (ASSEQ): entire post-baseline study period, aggregate of all available time points in the study with sequence data available
- Aggregated Post-Baseline Treatment Period (ATSEQ): entire post-baseline treatment period, aggregate of all available post-baseline time points during the treatment phase with sequence data available

Given only participants who are on stable NA treatment and who have HBV DNA <60 IU/mL at screening will be enrolled in this study, no baseline sequencing can be performed. In the exceptional case baseline HBV DNA levels are above the sensitivity limit of the sequencing assay used, the baseline sample may be sequenced.

#### 5.7.4.2. Definitions

- The presence of genetic variations is defined as changes (on the amino acid or nucleotide level) in the subject viral sequence compared to a HBV genotype specific reference viral sequence and/or the universal HBV reference sequence (NCBI ID X02763). The reference sequence to be used is provided in the database. The reference viral sequences to be used are:

Virus	Genotype	NCBI genbank accession	NGS isolate name	Sanger genbank accession	Sanger isolate name
HBV	A	X02763	adw2	X02763	adw2
HBV	B	AB219428	PNN3	D00329	pJDW233
HBV	C	GQ924620	M38	AB014362	03D03HCC
HBV	D	AF121240	11066	V01460	ayw
HBV	E	AB106564	GA325	X75657	ayw4
HBV	F	AY090458	70H	X75658	adw4q
HBV	G	AF160501	IG29227	AB064311	USG825
HBV	H	FJ356716	CL150171	AY090460	LAS2523
HBV	I	EU833891	H4536-07		

- Wild type: If at certain position the amino acid/nucleotide in the subject sequence matches the reference sequence, that is no genetic variation is present at that position, the virus is considered to be wild type at that position.

#### **5.7.4.3. Parameters to Analyze**

At specified time points and for each list specified in the section below, the following parameters will be analyzed:

- Number (%) of subjects with a substitution at a specific position.
- Number (%) of subjects with a specific substitution.
- Number (%) of subjects with a specific substitution profile
- Number (%) of subjects with substitutions on amino acid level (overall and by HBV genotype (A, B, C, D, E, F, G, H, I and Unknown))
  - at positions of interest in the RT-domain of the polymerase,
  - at positions of interest in the major hydrophilic loop of HBsAg.
- Number (%) of subjects with substitutions on nucleotide level
  - at the binding site positions of JNJ-3989 (i.e. JNJ-3976 and JNJ-3924) (overall and by HBV genotype (A, B, C, D, E, F, G, H, I and Unknown)).
  - in the precore (genome position 1896) and basal core promotor (genome positions 1762/1764) region (overall, by HBV genotype (A, B, C, D, E, F, G, H, I and Unknown))

The focus will be on substitutions at a time point, and reversion to wild type state. The above summaries will be repeated for genetic variations (not needed for CSR).

In the sequence analysis, sequences will be mapped to the respective genotype specific reference sequences after which nucleotide (nt) changes and amino acid (aa) substitutions will be annotated compared to the respective genotype specific reference (see Table in Section 5.7.4.2). In addition, the X02763 (HBV genotype A), which is the master reference sequence of the HBV database (db), will be used as universal reference sequence.

All NGS data will be collected using a nt and aa read frequency cut-off of  $\geq 0.01$ . For the analysis of nt changes and/or aa substitutions in terms of frequency of variant, a read frequency cut-off of  $\geq 0.15$  will be used. The persistence of nt changes and aa substitutions will be evaluated using a cut-off of  $\geq 0.15$  and  $\geq 0.01$ .

The applicability of the sequencing approach described here (e.g. the 0.01 sensitivity limit) will be assessed during the development program and might be adapted if needed.

#### 5.7.4.4. Positions & Genetic Variations of Interest

##### On the nucleotide level:

In the basal core promotor region:

- 1762 and 1764 (ECo numbering will be used)

In the precore region:

- 1896 (ECo numbering will be used)

In the basal core/precore region

- Combination of basal core promotor and/or precore region

In the JNJ-3989 binding pocket positions:

- JNJ-3976

Positions of Interest in the S gene: 261, 262, 263, 264, 265, 266, 267, 268, 269, 270, 271, 272, 273, 274, 275, 276, 277, 278, 279, 280.

- JNJ-3924

Positions of Interest in the X gene: 1781, 1782, 1783, 1784, 1785, 1786, 1787, 1788, 1789, 1790, 1791, 1792, 1793, 1794, 1795, 1796, 1797, 1798, 1799, 1800.

- In the JNJ-3976/JNJ-3924

Combination of JNJ-3989 binding site positions JNJ-3976 and/or JNJ-3924

##### Amino acid level:

In the pol/RT protein:

- 169, 173, 180, 181, 184, 194, 202, 204, 236, 250

See below breakdown of relative amino acid position of the 10 POI in the RT-domain of polymerase by HBV genotype.

HBV GT-A		HBV-GT-B/C/F/H/I		HBV GT-D		HBV-GT-E/G	
POL number	RT number	POL number	RT number	POL number	RT number	POL number	RT number
517	169	515	169	504	169	514	169
521	173	519	173	508	173	518	173
528	180	526	180	515	180	525	180
529	181	527	181	516	181	526	181
532	184	530	184	519	184	529	184
542	194	540	194	529	194	539	194
550	202	548	202	537	202	547	202
552	204	550	204	539	204	549	204
584	236	582	236	571	236	581	236

HBV GT-A		HBV-GT-B/C/F/H/I		HBV GT-D		HBV-GT-E/G	
598	250	596	250	585	250	595	250

In the major hydrophilic loop of the S-protein region (linked to vaccine escape):

- Amino acids 99 to 169
- Positions of interest: 116, 118, 120, 126, 129, 130, 131, 133, 134, 141, 142, 143, 144, 145, 164, 195, and 196.

#### 5.7.4.5. Analysis Methods

Frequencies and percentages will be presented at the time points specified above for the specified parameters. The denominator is the number of subjects with sequencing data at the selected time point.

A frequency output and/or figure will only be generated if number of participants with respective sequence information available (i.e. baseline sequence info for baseline outputs and paired baseline/post-baseline sequence info for post-baseline outputs) for that respective output or figure is greater or equal to 5 ( $N \geq 5$ ).

For comparison of amino acid or nucleotide levels to universal or genotype specific HBV reference sequences descriptive summaries may be performed by subgroups.

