5.1. Inclusion Criteria

Each potential participant must satisfy all of the following criteria to be enrolled in the study:

A01 (adapted from M01) Adult male or female participants ≥ 18 (or the legal age of consent in the jurisdiction in which the study is taking place) to 65 years of age, inclusive.

M02 Participants must be medically stable based on physical examination, medical history, vital signs, and 12-lead ECG performed at screening. If there are abnormalities, they must be consistent with the underlying illness in the study population. This determination must be recorded in the participant's source documents and initialed by the investigator.

A03 (adapted from M03a) Participants must have chronic HBV infection. HBV infection must be documented by serum HBsAg positivity at screening. In addition, chronicity must be documented by any of the following, at least 6 months prior to screening: serum HBsAg positivity, HBeAg positivity or HBV DNA positivity, ALT elevation above ULN without another cause than HBV infection, documented transmission event. If none of the above are available, the following ways of documenting chronicity are acceptable at the time of screening: liver biopsy with changes consistent with chronic HBV, or absence of marker for acute HBV infection such as positive immunoglobulin M (IgM) anti-hepatitis B surface (HBs) and anti-HBc antibodies.

Participants should:

- be HBeAg-negative, AND
- be anti-HBe antibody-positive, AND
- be on stable HBV treatment, defined as currently receiving NA treatment for at least 2 years prior to screening, and having been on the same NA treatment regimen (at the same dose) as used in this study for at least 3 months at the time of screening, AND
- have documented serum HBV DNA < 60 IU/mL on 2 sequential measurements at least 6 months apart (one of which is at screening), AND
- have documented ALT values $< 2.0 \times$ ULN on 2 sequential measurements at least 6 months apart (one of which is at screening).

M04 Participants must have a body mass index (BMI; weight in kg divided by the square of height in meters) between 18.0 and 35.0 kg/m², extremes included.

A05 (adapted from M05)	Participants must sign a Master ICF (specific for the Master Protocol PLATFORMPAHPB2001) and must sign the ICF specific for this intervention cohort, indicating that he or she understands the purpose of, and procedures required for, the study and is willing to participate in the study.

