##### 5.7.4.5.1. Post-Baseline

- Time of Virologic Breakthrough (if applicable)

For virologically suppressed participants who experience virologic breakthrough but who don't have baseline sequence information available, the frequency of genetic variations (with a primary focus on substitutions) at time of viral breakthrough will be tabulated in frequency outputs (n, %), based on NGS data (1% and 15% cut-off), for participants with viral sequence info available at time of viral breakthrough.

The return to wild type for subjects with virologic breakthrough and genetic variations at time of virologic breakthrough will be tabulated in frequency outputs based on NGS data, as well as the genetic variations in subjects who did not return to wild type.

- Time of Virologic /Clinical Flare (if applicable)

For virologically suppressed participants who experience virologic/clinical flare but who don't have baseline sequence information available, the frequency of genetic variations (with a primary focus on substitutions) at time of virologic/clinical flare will be tabulated in frequency outputs (n, %), based on NGS data (1% and 15% cut-off), for participants with viral sequence information available at time of flare.

The return to wild type for subjects with virologic/clinical flare and genetic variations at time of virologic/clinical flare will be tabulated in frequency outputs based on NGS data, as well as the genetic variations in subjects who did not return to wild type.

- **Time of Re-treatment during Post-treatment Follow-up**

For virologically suppressed participants who meet NA re-treatment criteria but who don't have baseline sequence information available, the frequency of genetic variations (with a primary focus on substitutions) at time of meeting NA re-treatment criteria will be tabulated in frequency outputs (n, %), based on NGS data (1% and 15% cut-off), for participants with viral sequencing information available at time of meeting NA retreatment criteria.

The return to wild type for subjects who meet re-treatment criteria during follow-up and genetic variations at time of meeting the re-treatment criteria will be tabulated in frequency outputs based on NGS data, as well as the genetic variations in subjects who did not return to wild type.

- **Other Post-Baseline**

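### The N≥5 rule for post-baseline sequencing tables counts baseline/post-baseline pairs, but the SAP expects no baseline sequences and plans those tables for participants who lack one

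*SAP*

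**What the plan says.** - **Output rule (SAP 5.7.4.5).** A frequency output or figure is generated only if the number of participants with the respective sequence information "for that respective output or figure is greater or equal to 5". For post-baseline outputs that information is defined as "paired baseline/post-baseline sequence info for post-baseline outputs".
- **Denominator (same section).** "The denominator is the number of subjects with sequencing data at the selected time point". No baseline sequence is required.
- **Baseline sequences (SAP 5.7.4.1).** Because of the HBV DNA entry requirement, "no baseline sequencing can be performed". One exception follows: "In the exceptional case baseline HBV DNA levels are above the sensitivity limit of the sequencing assay used, the baseline sample may be sequenced". The assay limit is not stated. The requirement itself is in Protocol 5.1, where participants must "have documented serum HBV DNA < 60 IU/mL on 2 sequential measurements at least 6 months apart".
- **Planned tables (SAP 5.7.4.5.1).** Frequencies of genetic variations at breakthrough, at virologic or clinical flare and at NA re-treatment are planned for participants without a baseline sequence. The breakthrough table is "for participants with viral sequence info available at time of viral breakthrough", and the other two follow the same pattern. Frequencies at other post-baseline time points are also planned, together with listings for all subjects.
- **Re-treatment time point (SAP 5.7.4.1).** Defined as "time point with sequence data available closest to time point where re-treatment criteria is met (See Section 5.4.1.1.1". SAP 5.4.1.1.1 defines NA treatment completion; NA re-treatment is 5.4.1.1.2.

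**The concern.** The output rule asks for something that the same part of the SAP says will not exist, and it applies that condition to tables designed for people who do not have it. A programmer following 5.7.4.5 would produce no table at breakthrough, flare or re-treatment. A programmer following 5.7.4.5.1 would produce all three if enough participants had sequences. The SAP does not say which section governs.

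The samples most likely to yield a sequence are those taken when HBV DNA rises, and these are the ones that the rule excludes from tabulation. Protocol 2.3.2.2.1 lists viral resistance to JNJ-3989 as a potential risk. Mutations over time are an exploratory endpoint, and Protocol 9.4.4 commits to tabulating and describing relevant genome changes. SAP Appendix 2 declares no change to protocol-planned analyses, so a rule that stops the tabulation would depart from the protocol without saying so.

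**Working it through.** The plan gives no figure to reproduce here. The check compares the sections and then tests whether the exceptional case could rescue the rule.

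**1. Tables at breakthrough, flare and re-treatment.** A pair needs a baseline sequence and a post-baseline sequence. These tables cover participants with no baseline sequence. Pairs = 0, the threshold is 5, and 0 < 5. This does not depend on the assay limit or on how many participants are sequenced at the event.

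**2. Other post-baseline frequency outputs.** These are not restricted to participants without a baseline sequence, so the exception in 5.7.4.1 could matter. Let q be the share of participants whose baseline sample can be sequenced. The documents do not give q, so the values below are assumptions. The chance of at least 5 baseline sequences among N participants is

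P = 1 − Σ (k = 0 to 4) C(N,k) q^k (1−q)^(N−k)

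| q (assumed) | N = 20 (assumed number with an event) | N = 34 (one arm) | N = 102 (all) |
|---|---|---|---|
| 0.5% | <0.001 | <0.001 | 0.0002 |
| 1% | <0.001 | <0.001 | 0.004 |
| 2% | <0.001 | <0.001 | 0.054 |
| 5% | 0.003 | 0.026 | 0.58 |

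These are upper bounds, because a pair also needs a post-baseline sequence. To expect 5 baseline sequences, q would have to be 5/102 = 4.9% with all arms pooled, or 5/34 = 14.7% within one arm. Only the pooled case with q near 5% gives the rule a reasonable chance of being met, and that is hard to square with baseline sequencing being described as exceptional.

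**3. Consistency within 5.7.4.5.** The denominator is everyone with a sequence at the time point. The output rule counts only those with a pair. A table could therefore have a denominator well above 5 and still not be produced.

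**4. Whether a pair is needed.** SAP 5.7.4.2 defines a genetic variation as a difference from a genotype-specific or universal reference sequence, and 5.7.4.3 annotates substitutions against the same references. The planned frequencies can be computed from the post-baseline sequence alone.

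**The case against.** The strongest reply is that SAP 5.7.4.5.1 is the specific provision and overrides the general rule. Its three event paragraphs are written for participants without baseline sequences and say that frequencies will be tabulated. The rule itself speaks of the information respective to each output, so a sensible programmer might apply N≥5 to the sequences that each table uses. This is a fair reading. However, the SAP does not state it, and the words in parentheses say the opposite, so the contradiction stands even though loss of the tables is not certain.

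Further points on that side:

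- **The number of pairs is not stated.** True: the assay limit is missing, and SAP 5.7.4 allows exploratory sequencing from HBV RNA, for which a baseline sample is scheduled. The documents do not say that RNA sequences would count as a baseline pair. Step 1 of the check holds regardless.
- **The practical gain is unknown.** Also true. Sequencing may be triggered at the sponsor virologist's request, and no number of sequenced events is projected. If fewer than 5 participants are sequenced at an event, the corrected rule gives no table either.
- **No data are lost.** This stands. SAP 5.7.4.5.1 and 5.7.4.5.2 provide listings, and SAP 5.7.4 promises a separate virology report; the rule names neither.
- **The wrong section number.** A reader might infer that the re-treatment sequence would be anchored to the NA completion assessment. The text does not support that: the time point is defined in words as when re-treatment criteria are met, and 5.7.4.5.1 repeats this. Only the number is wrong.

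**Conclusion.** The output rule in SAP 5.7.4.5 contradicts 5.7.4.1, 5.7.4.5.1 and its own denominator. Read literally, it suppresses the exploratory frequency tables at breakthrough, flare and NA re-treatment, because their paired count is 0 against a threshold of 5. For the other post-baseline tables the same outcome is likely but rests on an assumed q: with all 102 participants pooled, the chance of 5 or more baseline sequences is at most 0.054 for q up to 2%.

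A reader might go further and conclude that the resistance tables are certain to be lost, or that the resistance evidence is discarded. The documents do not support either. The conflict could be resolved in favour of 5.7.4.5.1, and the listings and virology report remain. What is established is a contradiction that, if left, would be settled by an analyst's choice.

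The primary and secondary endpoints, sample size, power and alpha are not affected.

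**What to change.** - **SAP 5.7.4.5.** For post-baseline outputs, require at least 5 participants with a sequence at that time point, which matches the section's own denominator. Keep the pairing condition only for outputs that use a baseline sequence.
- **Labelling.** Describe results without a baseline sequence as differences from the reference sequence, in line with the definition already in 5.7.4.2, and not as changes from baseline.
- **SAP 5.7.4.1 (clerical).** Change the re-treatment cross-reference from 5.4.1.1.1 to 5.4.1.1.2.

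The cost is a few wording edits in the SAP, with no new samples or assays. They should be made before the sequencing data are tabulated.
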